5.5.3 Management of Results

These NGS exploratory investigations will be performed solely for research purposes, as these assays are not as sensitive as the tests that are performed in a laboratory that is certified to perform genetic testing. There is no plan for looking for incidental findings that are relevant to other diseases. Therefore, results will not be shared with patients or referring physicians. Subjects will be contacted if a clinically actionable gene variant is discovered. Clinically actionable findings for this study are defined as disorders appearing in the American College of Medical Genetics and Genomics recommendations for the return of incidental findings that is current at the time of primary analysis. (A list of current guidelines is maintained on the CCR intranet: <https://ccrod.cancer.gov/confluence/display/CCRCRO/Incidental+Findings+Lists>).

5.5.4 Genetic Counseling

Subjects will be contacted with a request to provide a blood sample to be sent to a CLIA certified laboratory. If the research findings are verified in the CLIA certified lab, the subject will be offered the opportunity to come to NIH to have genetic education and counseling to explain this result; at the time of any such event(s), these activities will be funded by the NCI/CCR in consideration of the specific circumstances. If the subject does not want to come to NIH, a referral to a local genetic healthcare provider will be provided (at their expense).

This is the only time during the course of the study that incidental findings will be returned. No interrogations regarding clinically actionable findings will be made after the primary analysis.

5.6 EXPLORATORY/RESEARCH RADIATION EXPOSURE

An exploratory objective of this study is to describe the effects of the study treatment in tumor tissue with optional biopsies. To satisfy this exploratory objective, subjects will receive radiation from up to three (3) CT-guided biopsies for research purposes on this protocol.

CT-guidance may be used for up to three (3) optional tumor biopsies during the study. The procedures for performing each biopsy will follow clinical policies, no special procedures apply to the additional procedures for research purposes (see Section 5.2.4).

6 DATA COLLECTION AND EVALUATION

6.1 DATA COLLECTION

6.1.1 Summary

The PI will be responsible for overseeing entry of data into an in-house password protected electronic system (C3D) and ensuring data accuracy, consistency and timeliness. The principal investigator, associate investigators/research nurses and/or a contracted data manager will assist with the data management efforts. All data obtained during the conduct of the protocol will be

kept in secure network drives or in approved alternative sites that comply with NIH security standards. Primary and final analyzed data will have identifiers so that research data can be attributed to an individual human subject participant.

All adverse events, including clinically significant abnormal findings on laboratory evaluations, regardless of severity, will be followed until return to baseline or stabilization of event.

Document AEs from the first study intervention, Study Day 1 through 90 days after last treatment. Beyond the 90 day period after the last drug was administered, only adverse events which are serious and related to the study intervention need to be recorded.

End of study procedures: Data will be stored according to HHS, FDA regulations, and NIH Intramural Records Retention Schedule as applicable.

Loss or destruction of data: Should we become aware that a major breach in our plan to protect subject confidentiality and trial data has occurred, this will be reported expeditiously per requirements in section 7.2.1.

6.1.2 Data Collection/Recording Exceptions

6.1.2.1 Abnormal Laboratory Values

An abnormal laboratory value will be recorded in the database as an AE **only** if the laboratory abnormality is characterized by any of the following:

- Results in discontinuation from the study
- Is associated with clinical signs or symptoms
- Requires treatment or any other therapeutic intervention
- Is associated with death or another serious adverse event, including hospitalization.
- Is judged by the Investigator to be of significant clinical impact
- If any abnormal laboratory result is considered clinically significant, the investigator will provide details about the action taken with respect to the test drug and about the patient's outcome.

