8 SPONSOR SAFETY REPORTING

8.1 DEFINITIONS

8.1.1 Adverse Event

Any untoward medical occurrence in a patient or clinical investigation subject administered a

pharmaceutical product and which does not necessarily have a causal relationship with this treatment. An adverse event (AE) can therefore be any unfavorable and unintended sign (including an abnormal laboratory finding), symptom, or disease temporally associated with the use of a medicinal (investigational) product, whether or not related to the medicinal (investigational) product (ICH E6 (R2))

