10 STATISTICAL CONSIDERATIONS

10.1 STUDY ENDPOINTS

- Primary Endpoint:
 - The primary endpoint of this study is to determine the overall response rate (ORR) in patients with multiple myeloma treated with avelumab and irradiation.
- Secondary Endpoints:
 - The secondary endpoints are to determine:
 - Complete Response (CR) rate and Minimal Residual Disease (MRD) negative CR rate,
 - Reductions in bone marrow (BM) and peripheral blood (PB) plasmacytosis,
 - Radiographic reduction in size, and/or FDG avidity (PET/CT) of extramedullary lesions,

- Radiographic reduction in size, and/or FDG avidity (PET/CT) of non-irradiated extramedullary lesions (abscopal effect)
- Progression-free survival (PFS)
- Overall survival (OS)
- All Grade, Grade 3-4, and serious adverse events, and
- ORR post cycle 1 (prior to XRT)
- Exploratory Endpoints
 - Correlative Studies may be performed in select patients where adequate samples are available:
 - Peripheral blood mononuclear cells (PBMCs):
 - Changes in 123 immune subsets including CD4 and CD8 T cells, natural killer [NK] cells, NK-T cells, regulatory T cells [Tregs], myeloid-derived suppressor cells [MDSCs], and dendritic cells and 114 refined subsets relating to maturation/function using multicolor flow cytometry
 - Changes in the function of select immune cell subsets (e.g. CD4 and CD8 effector T cells, NK cells, Tregs, and MDSCs)
 - Changes in tumor antigen specific T cells (e.g. brachyury, MUC1, and CEA) using intracellular cytokine staining for IFN γ , TNF, and IL2 and the degranulation marker CD107a
 - Changes in T-cell clonality score using adaptive biotechnologies TCRseq assay
 - Changes in inflammatory gene signature using Nanostring's nCounter Human PanCancer Immune Profiling Panel
 - Plasma/Serum:
 - Changes in sCD27, sCD40L
 - Changes in cytokines (IFN- γ , IL-10, IL-12, IL-2, IL-4, etc.), chemokines, antibodies, tumor-associated antigens, and/or other markers
 - Changes in VDJ copy number of MM clones
 - Bone Marrow:
 - Changes in immune subsets
 - Changes in VDJ copy number of MM clones
 - DNA genetic alterations and TMB of MM cells

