15.3.4 Hepatic irAEs

Grade of Liver Test Elevation (NCI-CTCAE v5)	Initial Management	Follow-up Management

Grade 1 Grade 1 AST or ALT > ULN to 3.0 x ULN and/or Total bilirubin > ULN to 1.5 x ULN
	
Continue a velumab therapy
	
Continue liver function monitoring If worsens: Treat as Grade 2 or 3 to 4.

Grade 2 AST or ALT > 3.0 to ≤ 5 x ULN and/or total bilirubin > 1.5 to ≤ 3 x ULN
	
Withhold a velumab therapy Increase frequency of monitoring to every 3 days.
	
If returns to Grade ≤ 1: Resume routine monitoring; resume a velumab therapy. If elevation persists > 5 to 7 days or worsens: Treat as Grade 3 to 4.

Grade 3 to 4 AST or ALT > 5 x ULN and/or total bilirubin > 3 x ULN
	
Permanently discontinue a velumab therapy Increase frequency of monitoring to every 1 to 2 days 1.0 to 2.0 mg/kg/day prednisone or equivalent Add prophylactic antibiotics for opportunistic infections Consult gastroenterologist/hepatologist Consider obtaining MRI/CT scan of liver and liver biopsy if clinically warranted
	
If returns to Grade ≤ 1: Taper steroids over at least 1 month If does not improve in > 3 to 5 days, worsens or rebounds: Add mycophenolate mofetil 1 gram (g) twice daily If no response within an additional 3 to 5 days, consider other immunosuppressants per local guidelines.

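### The severe adverse-event endpoint stops at Grade 4, and asymptomatic, untreated Grade 3–4 laboratory values reach it only through investigator judgement; the effect is small and cheap to correct

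*Combined protocol and SAP*

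**What the plan says.** **Severe-AE endpoint.** Section 10.1 lists "All Grade, Grade 3-4, and serious adverse events" as a secondary endpoint. Section 10.4.3 summarises safety descriptively through AEs graded by CTCAE v5. No separate laboratory summary is described.

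**Other uses of severity.** The stopping rule in 10.4.4 counts Grade 3 or higher toxicity. It leaves out events that are clinically insignificant, resolve with conservative measures, or are not at least possibly due to treatment. The background rate in 1.2.8 is also for Grade 3 or higher.

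**Laboratory values.** Under 6.1.2.1, "An abnormal laboratory value will be recorded in the database as an AE" only if at least one condition applies:
- "Results in discontinuation from the study"
- clinical signs or symptoms
- "Requires treatment or any other therapeutic intervention"
- association with death or another serious AE
- "Is judged by the Investigator to be of significant clinical impact"

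A last bullet says that, for a result already considered clinically significant, "the investigator will provide details about the action taken with respect to the test drug".

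**Related text.** The AE definition in 8.1.1 expressly includes abnormal laboratory findings. Unacceptable toxicity is a reason to leave protocol therapy (3.8.1) but is not an off-study criterion (3.8.2). The study calendar (3.7) schedules blood counts and chemistry panels throughout treatment.

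**The concern.** There are two gaps in how severe toxicity is counted.

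First, the endpoint has an upper limit of Grade 4 and the stopping rule has none. A reader comparing the severe row with the stopping-rule tally, or with 1.2.8, would be comparing different quantities, and the most severe outcome would be absent from the row meant to show severe events.

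Second, the recording list for laboratory values contains no grade. Stopping or holding avelumab is not on it either, and the study-discontinuation criterion does not cover a drug stop, because 3.8 separates leaving therapy from leaving the study. For a Grade 3–4 value with no symptoms, no treatment and no link to a serious AE, the only route into the AE database is the investigator's judgement. Because safety is analysed only through recorded AEs, nothing later in the plan would show a value that was not recorded.

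At stake is the completeness and reproducibility of the severe-toxicity summary in a trial of 27 evaluable patients, where one reclassified patient is 1/27 = 3.7 percentage points. Any loss is downward.

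**Working it through.** **1. Reproduce the background rate.** Section 1.2.8: 177/1738 = 10.18%, stated as 10.2%. In 27 patients: 27 × 0.102 = 2.75 expected with a related event of Grade 3 or higher.

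**2. Count the itemised Grade 3 or higher related terms in 1.2.8.** These are subject-terms: one subject counted under one term. GGT is read as 10 subjects. In the order listed:

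17 + 17 + 10 + 10 + 8 + 7 + 6 + 6 + 5 + 5 + (5 × 4) + (10 × 3) = 141.

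**3. Laboratory terms.** Lipase 17, GGT 10, AST 8, anemia 6, CPK 6, ALT 4, amylase 4, hyponatremia 4, hypophosphatemia 4, lymphopenia 3, lymphocyte count 3, transaminase 3, hypokalemia 3. Total 75.

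**4. Remove terms the recording list cannot lose here.**
- Not on the panels listed in 2.2.4 and 2.4.2: lipase 17 + GGT 10 + CPK 6 + amylase 4 = 37. This leaves 75 − 37 = 38.
- Prednisone under Appendix C (15.3.4) at Grade 3–4, so the treatment criterion is met: AST 8 + ALT 4 + transaminase 3 = 15. This leaves 38 − 15 = 23.

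The 23 are anemia 6, hyponatremia 4, hypophosphatemia 4, hypokalemia 3, lymphopenia 3 and lymphocyte count 3.

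**5. Size.** 23/141 = 16.3%. Then 2.75 × 0.163 = 0.45 patient, and 0.45/27 = 1.7 percentage points. This treats every one of the 23 as asymptomatic, untreated, judged insignificant, and the patient's only severe event.

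**6. Check on the denominator.** 177 subjects had such an event but only 141 subject-terms are itemised, so at least 177 − 141 = 36 subjects fall outside the list. Against 177 the share is 23/177 = 13%, or 2.75 × 0.13 = 0.36 patient.

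**7. Sensitivity to the rate.** The endpoint in 10.1 is not limited to related events, and the documents give no severe-event rate for myeloma. If the true rate were 20% or 30% (assumptions) and the 16.3% share still applied, the ceiling would be 27 × 0.20 × 0.163 = 0.88 or 27 × 0.30 × 0.163 = 1.32 patients.

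**8. Grade 5.** Section 1.2.8 gives 4 related deaths in 1738. For 27 patients: 27 × 4/1738 = 0.06 expected. The mismatch is one of definition; few such events are expected.

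**The case against.** The strongest reply is that recording laboratory AEs by clinical significance is a stated convention, and that other text limits the loss. Most of this stands.

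- **Holds.** Section 3.4.1 allows dose delays only for adverse reactions at least possibly due to avelumab, and says that clinically insignificant laboratory values do not lead to delays. A value that caused a hold would usually have been judged significant already. Section 6.1.1 also treats clinically significant laboratory findings as AEs regardless of severity. But no rule makes a hold a recording trigger.
- **Grade 2 transaminases.** A reader might infer that a Grade 2 rise leading to a hold and to "Increase frequency of monitoring to every 3 days" drops out of the severe count. It cannot, since it was never Grade 3–4. If it persists beyond 5–7 days or worsens, 15.3.4 treats it as Grade 3–4, with prednisone, which meets the treatment criterion.
- **A quarter to a half of severe events lost.** The raw shares 38/141 (27%) and 75/141 (53%) invite this reading. The first includes steroid-treated liver terms; the second also includes tests not on this trial's panels.
- **Fatal events.** They are not lost. They remain under all-grade and serious events, in overall survival and, if at least possibly related, in the stopping rule.
- **Stopping rule.** It excludes clinically insignificant events by design, so it needs no change.
- **Disease effects.** A worst-grade table would mix myeloma with drug effect, since 2.1.1.8 admits neutrophils of 1000/mcL, platelets of 75,000/mcL and hemoglobin of 8 g/dL with transfusions. This is a fair point about the remedy and is met by showing the baseline grade.

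What survives is the difference in upper grade limit, and the dependence of asymptomatic, untreated Grade 3–4 values on judgement with no summary that would show them.

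**Conclusion.** The point holds as a modest reporting defect. As written, a fatal AE is outside the severe-grade row, and an asymptomatic, untreated Grade 3–4 value (for example lymphocyte count or an electrolyte) is in it only if the investigator judges it of significant clinical impact. The primary endpoint is unaffected.

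The laboratory effect is at most about 0.45 patient in 27, or 1.7 percentage points, at the 10.2% rate. That ceiling rests on the terms itemised in 1.2.8, on shares of subject-terms standing in for shares of patients, and on none of the 23 being recorded. The likely loss is smaller, since some anemia and electrolyte events would be treated or judged significant. The ceiling scales with the severe-event rate, which is not known for this population.

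A reader might go further and conclude that the trial's severe rate will be biased low against the 10.2%. The documents do not support that. They do not say how laboratory AEs were recorded in the pooled dataset, and a similar rule may have applied. The dataset is from other tumours, and no comparison with it is planned.

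**What to change.** 1. In 10.1, change the severe category from Grade 3–4 to Grade 3 or higher, with Grade 5 shown separately. This aligns the upper limit with 10.4.4.
2. In 10.4.3, add a descriptive table of baseline and worst post-baseline CTCAE v5 grade for each laboratory test, derived from values already collected and placed beside the AE tables. The baseline grade is needed because disease-related cytopenias are allowed at entry.
3. Optionally, add to 6.1.2.1 that a laboratory value leading to a hold or permanent discontinuation of avelumab is recorded as an AE. This mainly makes explicit what 3.4.1 implies.

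Leave 10.4.4 unchanged. The cost is one derived table and a wording change, plus one recording trigger if item 3 is adopted. No extra tests are needed. The reported severe rate may look slightly less favourable.

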6.1.2.2 Hospitalizations

Any cases of planned or prolonged hospitalization are not considered reportable serious adverse events if for the following reasons:

- Closer monitoring and/or prophylaxis of TLS at any cycle

6.2 DATA SHARING PLANS

6.2.1 Human Data Sharing Plan

What data will be shared?

I will share human data generated in this research for future research as follows:

- Coded, linked data in an NIH-funded or approved public repository.
- Coded, linked data in another public repository
- Coded, linked data in BTRIS (automatic for activities in the Clinical Center)
- Coded, linked or identified data with approved outside collaborators under appropriate agreements.

How and where will the data be shared?

Data will be shared through:

An NIH-funded or approved public repository. Insert name or names: [ClinicalTrials.gov](https://clinicaltrials.gov), dbGaP.

BTRIS (automatic for activities in the Clinical Center)

Approved outside collaborators under appropriate individual agreements.

Publication and/or public presentations.

When will the data be shared?

Before publication.

At the time of publication or shortly thereafter.

6.2.2 Genomic Data Sharing Plan

Unlinked genomic data will be deposited in public genomic databases such as dbGaP in compliance with the NIH Genomic Data Sharing Policy.

6.3 RESPONSE CRITERIA

Patient response and overall response rates (ORR) will be assessed according to the 2016 International Myeloma Working Group (IMWG) response criteria.[\[1\]](#) (See [Appendix F](#).)

6.3.1 Best Overall Response

The best overall response is the best response recorded from the start of the treatment until disease progression/recurrence per IMWG criteria.

6.3.2 Duration of Response

The duration of response (DoR) is measured from the time measurement criteria are met for a response of PR or better until the first date that recurrent or progressive disease is objectively documented. Patients without a progression event will be censored at the date response assessment was last evaluated.

6.3.3 Progression-Free Survival

Progression-free survival (PFS) is defined as the duration of time from the date of study enrollment until time of disease progression, or death, whichever occurs first. Patients without a progression or death event will be censored at the date response assessment was last evaluated. Note that, a progression or death event occurring up to cycle 2 day 1 will not be included in the definition as patients have not had received combination therapy until that time.

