3.5.1 Cycle 2 Day 1 Evaluation

We hypothesize that avelumab monotherapy will not be sufficient and that concomitant administration of XRT will be needed for synergy and clinical responses. Therefore, at the Cycle 2 Day 1 evaluation, if the patient meets criteria for biochemical progression per IMWG, the patient will remain on treatment if clinically stable and without overt clinical progression in the judgement of the investigator. In terms of evaluating best response, PD on Cycle 2 Day 1 and treatment continuation will not be included.

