3.5.2 Treatment Past Progression (“Pseudo-progression”)

Patients will not be allowed to remain on treatment past IMWG defined PD unless per the investigator they are receiving objective clinical benefit.

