6.3.4 Overall Survival

Overall survival (OS) is defined as the duration of time from the date of study enrollment until time of death. Patients without a death event will be censored at the date survival assessment was last evaluated (e.g., clinic visit, phone call).

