10.3 POPULATIONS FOR ANALYSES

Modified intention to treat: all patients who receive at least one dose of avelumab will be included in the statistical analyses performed.

10.3.1 Evaluable for toxicity:

All patients will be evaluable for toxicity from the time of their first treatment with avelumab.

10.3.2 Evaluable for objective response:

Only those patients who have measurable disease present at baseline and have received at least one dose of therapy will be considered evaluable for response.

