10.4.3 Analysis of the Secondary Endpoints

- CR rate: the fraction of patients who experience a CR or sCR using the study treatment will be determined by dividing the number of these responders by the total evaluable patients. The fraction will be reported along with 90% and 95% two-sided confidence intervals.
- MRDnegCR rate: the fraction of patients who experience an MRDnegCR using the study treatment will be determined by dividing the number of these responders by the total evaluable patients. The fraction will be reported along with 90% and 95% two-sided confidence intervals.
- Reduction of BM and PD plasmacytosis: Percent change in plasma cells in the PB and BM from baseline will be reported descriptively.

- Reduction of size, and/or FDG avidity of extramedullary lesions: Percent reduction of size, and/or FDG avidity, radiographically, of extramedullary lesions compared to baseline will be reported descriptively.
- PFS: will be determined using the Kaplan-Meier method, considering those who progress or die without progression as failures, and censoring those who do not.
- OS: will be determined using the Kaplan-Meier method.
- Safety and tolerability: overall tolerability in terms of adverse events will be evaluated with descriptive statistics to determine the safety of receiving avelumab in the context of irradiation in RRMM patients. NCI CTCAE v.5 will be used to grade adverse events.
- ORR post cycle 1: a milestone ORR at start of cycle 2 will be calculated as above to determine ORR of avelumab monotherapy after 1 cycle of therapy.

Each of these will be calculated starting from the date the patient enrolled onto the trial which corresponds to the date the patient signed the informed consent document. Appropriate confidence intervals will be reported for each of these measures. (Only PFS events occurring during the initiation and of the combination of irradiation and avelumab and after will be counted as this proof of principal study hypothesis is that the combination of BavXRT will be active.)

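### PFS is timed from consent but ignores progressions and deaths up to Cycle 2 Day 1, so a Cycle 1 death lowers OS but not PFS, and PFS is biased upward by every early failure not recorded again

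*Combined protocol and SAP*

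**What the plan says.** Section 6.3.3 defines PFS from study enrollment to progression or death. Section 10.4.3 fixes that date: the secondary measures are calculated "starting from the date the patient enrolled onto the trial which corresponds to the date the patient signed the informed consent document".

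Section 6.3.3 then adds that "a progression or death event occurring up to cycle 2 day 1 will not be included in the definition", giving as its reason that the combination has not yet been received. Section 10.4.3 closes with its own version: "Only PFS events occurring during the initiation and of the combination of irradiation and avelumab and after will be counted". The Kaplan-Meier bullet for PFS in that same section treats everyone who progresses or dies as a failure and makes no exception. No section moves time zero.

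Four other provisions matter:

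- **OS (6.3.4):** "Overall survival (OS) is defined as the duration of time from the date of study enrollment until time of death". There is no exclusion window.
- **Analysis set (10.3):** "all patients who receive at least one dose of avelumab will be included in the statistical analyses performed". Patients who fail in Cycle 1 therefore stay in.
- **Censoring (6.3.3):** "Patients without a progression or death event will be censored at the date response assessment was last evaluated". Nothing is said about a patient whose only event is an excluded one.
- **Continuation:** at Cycle 2 Day 1, "if the patient meets criteria for biochemical progression per IMWG, the patient will remain on treatment if clinically stable and without overt clinical progression" (3.5.1). Otherwise, "Patients will not be allowed to remain on treatment past IMWG defined PD unless per the investigator they are receiving objective clinical benefit" (3.5.2).

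**The concern.** The clock and the events do not match. Every analysed patient carries the time from consent to Cycle 2 Day 1, including a 4-week avelumab lead-in, during which no PFS event can be counted. The result is neither PFS from enrollment nor a landmark PFS from the start of the combination.

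Under the most natural reading of 10.3 and 6.3.3 together, a patient who dies in Cycle 1 stays in the set, has no counted event, and is censored as progression-free. The same death counts in OS. The PFS curve can then lie above the OS curve, which is impossible when death is always a PFS event.

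At stake is the reading of a secondary endpoint in at most 27 evaluable patients. A reader shown PFS from enrollment would take it at face value. How each early failure is handled would be settled at analysis, with the data in view.

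**Working it through.** **Inputs.** Total n = 27 and first-stage n = 13 (10.2). Lead-in of 28 days (Précis). Time origins, exclusion, censoring and analysis set as set out above. The plan states no PFS figure, so there is none to reproduce. Its one related figure, early termination under the 5% null, checks: 0.95^13 = 0.513, as stated in 10.2. It does not depend on PFS.

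**1. OS against PFS, no hazard assumption.** With d Cycle 1 deaths in 27 and no other early events, OS at Cycle 2 Day 1 is (27-d)/27:
- d = 1: 26/27 = 96.3%
- d = 2: 25/27 = 92.6%

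PFS at the same time is 100% in both cases.

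**2. Later PFS estimates, no hazard assumption.** Suppose k of n dosed patients fail up to Cycle 2 Day 1 and nobody else is censored before then. Counting all events, S(t) = [(n-k)/n] × S(t given event-free at Cycle 2 Day 1). If the k are dropped or censored, the first factor disappears, so the estimate is multiplied by n/(n-k).

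| n | k | Factor | A true 40% is reported as |
|---|---|---|---|
| 27 | 1 | 27/26 = 1.04 | 41.5% |
| 27 | 2 | 27/25 = 1.08 | 43.2% |
| 27 | 3 | 27/24 = 1.13 | 45.0% |

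If the trial stops at 13, the factors for k = 1, 2, 3 are 13/12 = 1.08, 13/11 = 1.18 and 13/10 = 1.30.

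**3. Which early failures are lost.**
- *Deaths:* always lost, because they cannot recur.
- *Biochemical progression at Cycle 2 Day 1 in a stable patient:* treatment continues (3.5.1), and the Study Calendar (3.7) schedules a disease reassessment at Cycle 2 Day 15, where it can be recorded again.
- *Overt progression:* normally ends therapy (3.5.2, 3.8.1). The patient may still be seen at the end-of-treatment and 30-day safety visits (3.6.1, 3.7, 3.8). The plan does not say whether PFS is then censored, re-dated, or carried to a later death.

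**4. Illustration for the median.** Assume constant hazard, true median m of 2 to 4 months, lead-in L = 28/30.44 = 0.92 months, and a share f of early failures lost with the rest recorded at Cycle 2 Day 15. With S(L) = 0.5^(L/m), the reported median is where S(t) = 0.5 × [1 - f(1-S(L))], so the shift is m × log2{1/[1 - f(1-S(L))]}. The early-failure share 1-S(L) is about 27% for m = 2 and 15% for m = 4.

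| Share lost | Shift in median (months) |
|---|---|
| none | 0 |
| 10% | +0.08 to +0.09 |
| 25% | +0.20 to +0.22 |
| 50% | +0.42 to +0.44 |
| all | +0.92 |

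The all-lost value is simply the lead-in length, a product of constant hazard. With all lost and a Weibull hazard, it is +0.3 to +0.4 if the hazard rises (shape 1.5) and +1.9 to +2.2 if it falls (shape 0.7). Time from consent to first dose moves both curves equally and does not add to the shift.

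**5. The two cut-offs.** An event on Cycle 2 Day 1 itself is excluded by 6.3.3, yet 10.4.3 counts events during initiation of the combination. Section 3.3.2 also lets radiation move by up to 7 days either way. If radiation starts early, events between its start and Cycle 2 Day 1 count only under 10.4.3. If it starts late, events after Cycle 2 Day 1 but before radiation count only under 6.3.3.

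**The case against.** The exclusion is deliberate, stated twice, and reasoned: the hypothesis concerns the combination. PFS is a descriptive secondary endpoint in a single-arm pilot, with no PFS threshold or comparator, and OS captures every Cycle 1 death. All of that stands and limits the consequence. It does not justify the clock: a combination-only target calls for time zero at the start of the combination.

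Three stronger readings are tempting, and the documents do not support them.

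- **A reader might infer that every early progression vanishes because contact after progression is for survival only.** Section 3.6.4 says so subject to investigator judgement, and the safety visits in 3.6.1, 3.7 and 3.8 carry no exemption for progression. Later deaths also count as failures. What is missing is a rule, not necessarily the data.
- **A reader might take a median shift of about a month as the expected bias.** That requires every early failure to be lost, contrary to 3.5.1 and the Cycle 2 Day 15 reassessment. A biochemical progression recorded again there is dated about 14 days late and leaves later estimates unchanged.
- **A reader might infer that PFS will exceed OS throughout.** It does so only while uncounted Cycle 1 deaths outweigh the progressions that are counted.

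**Conclusion.** The point holds. As written, the rule leaves time zero and the counted events mismatched, lets a Cycle 1 death lower OS without touching PFS, and biases PFS upward for every early failure not recorded again. The n/(n-k) factors need only that the k failures are dropped or censored and that no one else is censored before Cycle 2 Day 1.

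The size is not established, because the documents give neither an early-failure rate nor a PFS assumption. Under the constant-hazard illustration, the median shift is 0 if none are lost, about +0.1 to +0.4 months if 10% to 50% are lost, and at most about +0.9 if all are lost. The differing cut-offs in 6.3.3 and 10.4.3 are a smaller defect of the same kind. The response-rate endpoint, the two-stage design and the go/no-go rule are untouched. It should be corrected before analysis, but it does not threaten the trial's main conclusion.

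**What to change.** Choose one of two.

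1. **Count everything.** Delete the last sentence of 6.3.3 and the closing parenthesis of 10.4.3, and count all progressions and deaths in the modified intention-to-treat set. First dose is the better origin because that set is defined by dosing. If enrollment is kept to match OS, note that the time from consent to first dose is event-free by construction. Add a sensitivity analysis for biochemical progression at Cycle 2 Day 1 in patients continued under 3.5.1.
2. **Label a landmark PFS.** Set time zero at one explicit start-of-combination date, used in both sections, among patients event-free at that date. State whether progression found at the Cycle 2 Day 1 evaluation falls before or after it. Report earlier failures by type: death, overt progression, biochemical progression.

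Both are wording changes and need no new data. Option 1 adds one sensitivity analysis and gives a less favourable PFS. Option 2 adds a short table and describes only patients who reach the combination.
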